07/25/2023

**THE UNDERESTIMATED UTILITY OF RESTING-STATE GAMMA
OSCILLATIONS: BOTH INCREASE AND DECREASE OF GAMMA
DISCRIMINATES EARLY-ONSET ALZHEIMER'S DISEASE PATIENTS FROM
HEALTHY INDIVIDUALS**

STUDY PROTOCOL:

- **EEG Recording and Analysis**

Instructions Prior to Experiment and EEG Recording Environment

- Participants were asked not to consume any caffeine prior to experiments.
- EEG was recorded in a sound-attenuated and electrically shielded room.

EEG Recording Setup

- EEG was amplified using a BrainAmp 32-channel DC amplifier
- EEG was bandpass-filtered between 0.03-70 Hz and digitized at a sampling rate of 500 Hz (Brain Products GmbH; Gilching, Germany).
- EEG was recorded from 30 Ag/AgCl electrodes (Figure 1).
- Electrodes were positioned on an elastic cap according to the international 10-20 system (EasyCap; Brain Products GmbH; Gilching, Germany).
- All electrodes were referenced to linked earlobes (A1+A2).
- Electrooculograms (EOG) were recorded from two additional electrodes.
- Electrode impedances were kept below 10 k Ω .
- EEG recordings were performed during morning hours (approximately between 09.00 to 10.00 am)
- EEG recordings lasted 8 minutes (4 minutes: eyes open & 4 minutes: eyes closed).

[figure not shown]

Figure 1. EasyCap layout for 30 Electrodes (EasyCap; Brain Products GmbH; Gilching, Germany)

EEG Data Preprocessing

Brain Vision Analyzer v.2.2 (Brain Products GmbH; Gilching, Germany) program was used for offline data analysis. EEG preprocessing was employed as below;

- The continuous EEG data were resampled to a 256 Hz sampling rate.
- A band-pass filter at 0.1 with a 12 dB/octave slope and a 50 Hz notch filter was applied.
- Vertical and horizontal ocular artifacts were corrected with independent component analysis (ICA) with the Infomax algorithm using default parameters.
- Four minutes eyes-closed recordings were segmented into six-second epochs.

- Artifacts that still contaminated the EEG data (i.e., muscle artifacts and drowsiness) were semi-automatically rejected based on maximum voltage steps of 50 $\mu\text{V}/\text{ms}$, amplitudes exceeding $\pm 70 \mu\text{V}$, and activity below 0.5 μV parameters.

Power Spectral Analysis

A Fast Fourier Transform (FFT) was applied with

- Maximum resolution power,
- Non-complex output on full-spectrum,
- 10% Hanning window function

Coherence Analysis

- The Laplacian Current Source Density transformation with an order of splines 4, the maximal degree of Legendre polynomials 10 and 1×10^{-5} Lambda was applied.
- The FFT with maximum resolution voltage, no window function, and complex output on the half spectrum was computed.
- The imaginary part of coherency was used to evaluate connectivity between hemispheres, within hemispheres, and midline connectivity.

● **MRI Acquisition**

- Philips Achieva 1.5 Tesla scanner was used.
- Scans were performed according to the Alzheimer's disease Neuroimaging Initiative (ADNI, www.adni.loni.usc.edu).
- The pre-processing of images was performed with the SPM12 software package.
- The gray matter volumes and cortical thickness were obtained from the 3D-T1 weighted TFE sequence (TR: 9ms, TE: 4ms, FOV: 240mm, matrix: 256, slice thickness: 1mm, NSA: 1).
- Mean gray matter volumes (GMVs) inside ROIs were estimated using the LPBA40.
- The total intracranial volume (TIV) for each participant is calculated and exported. GMVs were normalized according to each individual's TIV to remove the effect of different brain sizes.

STATISTICAL ANALYSIS PLAN (SAP)

- **For EEG Analysis:**

The following EEG measures were analyzed using separate repeated-measures ANOVA including group as a between-group factor and different within-subject factors for;

(1) the EEG power [*anterior-posterior distribution* (frontal, central, parietal, and occipital) and *laterality* (left, midline, and right)];

(2) EEG intra-hemispheric ICoh measures [*region* (14-levels) and *hemisphere* (left and right)];

(3) midline-to-lateral ICoh measures [*midline region* (4-levels), *lateral region* (8-levels) and *hemisphere* (2-levels)];

(4) midline-to-midline ICoh measures [*midline region* (3-levels)];

(5) inter-hemispheric ICoh measures [*region* (10-levels)].

All analyses were performed for total gamma and sub-gamma frequency bands.

When Mauchly's test indicated that the assumption of sphericity had been violated, the Greenhouse-Geisser correction was applied where $\varepsilon < 0.75$, and the Huynh-Feldt correction was applied where $\varepsilon > 0.75$.

- **For EEG Analysis:**

GMV measures were analyzed with univariate ANOVA. Age and gender variables were included in the analysis as covariates. Bonferroni correction was applied for 54 GMV ROIs. The significance level was set to $P < 0.0009$.

- **For Correlations Analysis:**

Correlations between CSF, NPT, EEG, and MRI parameters were analyzed with Pearson correlation analysis. In order to minimize the number of false positives in correlation analysis, a Benjamin-Hochberg false discovery rate (FDR) was used to control the type-I error.

- **For Discriminant Analysis:**

The discriminant analysis was performed including the group as the dependent variable and a total of four independent variables (three electrode pairs from coherence and one electrode from power analysis) to the model. The analysis was performed with the enter method.

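### The coherence FFT is run without a taper on epochs that keep activity down to 0.1 (Hz assumed), so very slow activity can leak into the gamma bins and shrink gamma ICoh by an amount the documents do not let one determine

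*Combined protocol and SAP*

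**What the plan says.** Power and coherence share the steps under EEG Data Preprocessing in the study protocol. "The continuous EEG data were resampled to a 256 Hz sampling rate". The filter line reads: "A band-pass filter at 0.1 with a 12 dB/octave slope and a 50 Hz notch filter was applied". No unit is printed after 0.1, and I read it as Hz. "Four minutes eyes-closed recordings were segmented into six-second epochs". Epochs beyond ±70 µV are rejected.

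The two paths then separate. Under Power Spectral Analysis the FFT uses a "10% Hanning window function". Under Coherence Analysis a spatial transform comes first ("The Laplacian Current Source Density transformation with an order of splines 4"), and then: "The FFT with maximum resolution voltage, no window function, and complex output on the half spectrum was computed". Connectivity is measured by the imaginary part of coherency.

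No reason is given for the different windows, and no detrending or leakage check is described. The documents do not give the limits of the gamma bands, the spectral slope, slow or gamma power by group, or whether ICoh is signed or absolute.

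In the SAP, gamma ICoh is the outcome in four of the five repeated-measures ANOVA families (items 2 to 5), and it supplies three of the four predictors in the discriminant analysis.

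**The concern.** An FFT treats each epoch as if its end joined its beginning. If the two ends differ, the jump spreads power across all frequencies, falling only as about 1/f². Activity is kept down to about 0.1 Hz, a period of 10 s, so a six-second epoch can hold less than one slow cycle and end far from where it began. The ±70 µV limit still allows an end-to-end step of up to 140 µV before the Laplacian. That transform acts across electrodes and does not taper the epoch in time.

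Gamma power is weak, so leaked slow power can be a visible share of what is measured there. The leading leakage term has the same phase in both channels. It enters the autospectra, which form the ICoh denominator, and the real cross-spectrum, but mostly not the imaginary part. ICoh then shrinks toward zero, more so in a participant with a higher slow-to-gamma ratio. If that ratio differs between groups, part of a group difference in gamma ICoh could reflect leakage and not coupling. No planned analysis would detect this.

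**Working it through.** The documents state no leakage or ICoh figure, so there is nothing of theirs to reproduce.

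**Inputs from the protocol.** 256 Hz × 6 s = 1536 samples per epoch; at most 240/6 = 40 epochs; high-pass 0.1 Hz (unit assumed) at 12 dB/octave; no window for coherence, 10% Hanning for power.

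**Assumptions.** Power-law spectra 1/f^b with b from 1 to 2.5; gamma taken as 30-45 Hz (30-48 Hz in the simulation); true ICoh 0.30; the current source density step not modelled.

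**Step 1, formula.** ICoh = Im(Sxy)/√(Sxx·Syy). If leakage L is added to a true gamma density G in both autospectra and not to Im(Sxy), ICoh is multiplied by 1/(1 + L/G).

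**Step 2, convolution.** Each assumed spectrum was convolved with the spectral window of the epoch and averaged over 30-45 Hz.

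| Slope b | Autospectrum, no window (true = 1) | ICoh, no window | ICoh, 10% Hanning |
|---|---|---|---|
| 1 | 1.00 | 0.299 | 0.30 |
| 1.5 | 1.02 | 0.294 | 0.30 |
| 2 | 1.22 | 0.246 | 0.30 |
| 2.5 | 4.46 | 0.067 | 0.30 |

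**Step 3, which slow activity matters.** At slope 2, starting from 0.246:
- doubling all power below 8 Hz gives 0.209, and (0.246 − 0.209)/0.246 = 15%;
- doubling only 0.5-8 Hz gives 0.239, or about 3%;
- doubling only 1-8 Hz gives 0.243, or about 1%.

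In terms of inflation (0.30/ICoh), these go from 1.220 to 1.435 for everything below 8 Hz and to 1.235 for 1-8 Hz alone. So (0.215 − 0.015)/0.215 = 93% of the leakage from below 8 Hz comes from below 1 Hz. Consistently, a 1 Hz high-pass brings the slope-2 factor at 40 Hz from 0.83 to 0.98.

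**Step 4, gamma power.** The ratio also moves with its denominator. At slope 2 the excess is 0.22. Halving gamma power with slow activity fixed doubles it: 0.30/1.44 = 0.208. Doubling gamma power halves it: 0.30/1.11 = 0.270.

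**Step 5, simulation by a different route.** Two channels, 40 epochs, 1/f² slow activity high-passed at 0.1 Hz, 20 simulated participants per setting. Slow SD and gamma density are assumptions. Mean ICoh without a window:

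| Gamma density (µV²/Hz) | Slow SD 5 µV | 10 µV | 20 µV | 30 µV |
|---|---|---|---|---|
| 0.003 | 0.264 | 0.203 | 0.108 | 0.059 |
| 0.01 | 0.288 | 0.262 | 0.201 | 0.146 |
| 0.1 | 0.298 | 0.293 | 0.283 | 0.263 |

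With the 10% taper every cell lies at 0.295-0.300 after the same rounding, apart from one at 0.302.

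**Step 6, exceptions.** With a true ICoh of 0, signed ICoh stays near 0 and mean absolute ICoh stays near its 40-epoch floor (0.089 with almost no slow activity, 0.082 at slow SD 20 µV). Phase-lagged 10 Hz activity leaks a spurious signed ICoh of about ±0.03 without a window and none with the taper.

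**Step 7, the rejection limit.** Slope 2.5 carried down to 0.1 Hz implies a broadband SD of about 29, 52, 90 and 165 µV for 40 Hz densities of 0.003, 0.01, 0.03 and 0.1 µV²/Hz. At 0.01 or more, few epochs would pass ±70 µV. For slope 2 the variance is density × 40² × (π/(2√2))/0.1. At 0.01 this is 0.01 × 1600 × 1.111/0.1 = 178, an SD of 13 µV, so the limit does not exclude slope 2 at that density.

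**The case against.** The strongest case against is that the effect may be trivial here. At slopes 1 and 1.5 the loss is 2% or less. The slope-2.5 figure may conflict with the protocol's own amplitude limit. The Laplacian can change each channel's slow-to-gamma ratio, and no figure above models it. All of this stands, and it means that no size can be attributed to this study.

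A reader might infer that ordinary delta or theta slowing in patients would by itself create a false gamma ICoh decrease. The documents do not support that. They report no slow activity by group, and doubling 1-8 Hz power moves ICoh by only about 1% at slope 2. The 15% figure requires activity below 1 Hz to double as well.

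A reader might also infer that leakage always lowers ICoh. It shrinks a non-zero value toward zero, which for a negative signed ICoh is a rise, and lagged rhythms can add a spurious value of either sign.

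Nor do different windows by themselves invalidate anything: power and coherence go into separate ANOVAs and enter the discriminant model as separate predictors, so no analysis needs a common window.

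None of this supplies a reason for leaving out the taper. For a true non-zero ICoh, the untapered convolution estimate was not closer to the truth at any slope tested.

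**Conclusion.** The point holds as a weakness of stated method with a cheap remedy. It does not show that any coherence result is wrong. Without a taper, gamma ICoh can be attenuated: by under 1% at slope 1, about 2% at slope 1.5 and about 18% at slope 2 ((0.30 − 0.246)/0.30), with much larger losses at slope 2.5 that may not be compatible with the rejection limit. These figures assume power-law spectra down to 0.1 Hz, a 30-45 Hz band, a true ICoh of 0.30 and no effect of the current source density step.

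Bias between groups is conditional. It needs a difference in activity below about 1 Hz or in gamma power. The study's title speaks of gamma both increasing and decreasing, without saying in which measure, so the second route deserves a check; the documents establish neither.

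**What to change.** Apply the 10% Hanning window already specified for the power FFT to each epoch before the coherence FFT, and recompute all ICoh measures, the four ICoh ANOVA families and the discriminant analysis. If the results do not change materially, say so and the matter is closed. If they do, base the coherence conclusions on the tapered analysis.

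The cost is one software setting and a re-run on existing data. The taper down-weights the epoch edges: the retained share is 1 − (5/8)(0.10) = 0.94, so about 6% of the effective data is given up.

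### The TIV normalisation formula is not stated and TIV is not a covariate in the 54 GMV models; if GMV was divided by TIV, some head-size effect may remain

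*Combined protocol and SAP*

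**What the plan says.** The protocol's MRI Acquisition section describes head-size handling in two sentences: "The total intracranial volume (TIV) for each participant is calculated and exported", and "GMVs were normalized according to each individual's TIV to remove the effect of different brain sizes". It does not say whether the normalisation is a ratio, a regression residual or something else.

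The GMV paragraph of the SAP stands under the second of two identical *For EEG Analysis* headings, apparently a labelling slip with no bearing here. It says "GMV measures were analyzed with univariate ANOVA", then "Age and gender variables were included in the analysis as covariates", then "Bonferroni correction was applied for 54 GMV ROIs", with a per-test level of P < 0.0009. TIV is not among the listed covariates.

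The documents contain no check that normalised GMV is unrelated to TIV, no comparison of TIV between groups, no matching, no sensitivity analysis with TIV in the model, and no sample size.

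**The concern.** The stated purpose is to take brain size out of the comparison. Division by TIV does that only if a 1% larger TIV goes with 1% more regional GMV. If the slope is lower, the ratio over-corrects, and people with larger heads get smaller normalised volumes. A model without TIV cannot absorb what is left. The gender covariate takes out only the between-sex part.

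Two separate consequences follow:

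- **Lost precision.** This needs only a slope different from 1.
- **Bias.** This also needs a TIV difference between the groups after adjustment for age and gender. Patients and healthy controls are not randomised, so balance is not assured, but nothing in the documents shows an imbalance.

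**Working it through.** **Inputs from the documents:** 54 ROIs; per-test level 0.0009; covariates age and gender; TIV available for each participant.

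**Assumed inputs:** 20 per group, TIV CV 8%, GMV CV 10%, slope *b* of log GMV on log TIV from about 0.4 to 1, group gap in TIV of 0, 3% or 5% after adjustment for age and gender.

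**1. The plan's own figure.** With an implied family level of 0.05, 0.05/54 = 0.000926, which rounds to 0.0009. The threshold reproduces and is not in question.

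**2. Bias if the normalisation is a ratio.** If log GMV = *b* × log TIV + group effect + error, then log(GMV/TIV) = (*b* − 1) × log TIV + group effect + error. The false group difference is (*b* − 1) × gap:

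- *b* = 0.5, gap 3%: −0.5 × 3% = −1.5%
- *b* = 0.5, gap 5%: −0.5 × 5% = −2.5%
- *b* = 1: zero, whatever the gap

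**3. False positives at the SAP's threshold.** The GMV-TIV correlation is *r* = *b* × 8/10 = 0.4 at *b* = 0.5. In squared per cent, the ratio's variance is 10² + 8² − 2 × 0.4 × 10 × 8 = 100, so its SD is 10%. The standard error of the group difference is 10 × √(2/20) = 3.16%. The noncentrality is 1.5/3.16 = 0.47 or 2.5/3.16 = 0.79, with 40 − 4 = 36 df. A two-sided test at 0.0009 then rejects about 0.2% or 0.5% of true nulls, against 0.09%. Simulation of the 5% gap agrees: bias about −2.5% and rejection about 0.5% with the ratio, bias near zero and about nominal error with TIV as covariate.

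For scale, 80% power at this threshold needs a noncentrality of about 4.51, a true difference of 4.51 × 3.16 = 14%.

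**4. Precision with balanced TIV.** Ratio variance is 164 − 160*r*; variance with TIV as covariate is 100(1 − *r*²). Power starts from an ROI with 80% under the ratio; the noncentrality is multiplied by the square root of the variance ratio, with 35 df.

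| *r* | slope = *r* × 10/8 | ratio | covariate | ratio ÷ covariate | power with TIV covariate |
|---|---|---|---|---|---|
| 0.3 | 0.375 | 116 | 91 | 1.27 | 91% |
| 0.4 | 0.5 | 100 | 84 | 1.19 | 89% |
| 0.6 | 0.75 | 68 | 64 | 1.06 | 83% |
| 0.7 | 0.875 | 52 | 51 | 1.02 | 81% |
| 0.8 | 1.0 | 36 | 36 | 1.00 | 80% |

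Charging also for estimating the TIV slope lowers the figures for *r* = 0.3, 0.4 and 0.6 to about 90%, 87% and 82%.

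**5. Price of the covariate when TIV is unbalanced.** A 5% gap is *d* = 5/8 = 0.625 SD. Collinearity multiplies the variance of the group effect by 1 + *d*²/4 = 1.098, about 10%. At slope 0.75 the net variance ratio is 1.0625/1.098 = 0.97, so power is about 78% against the ratio's 80% for the same effective signal. The ratio's estimate is biased in that setting, so its power is not a clean benchmark.

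**6. If GMV was instead residualised on TIV in the pooled sample.** Proportionality is then not needed, but testing the residuals without TIV in the model shrinks the group effect by 1 − *R*², where *R*² is the squared correlation of group with TIV. At *d* = 0.625, *R*² = 0.0977/1.0977 = 0.089, so a 13% effect becomes 13 × 0.911 = 11.8% in large samples; simulation with 20 per group gave about 11.6%. Adding TIV to the model corrects this too.

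**7. Sensitivity to other assumptions.** A separate simulation used 30 per group, residual GMV CV 8%, within-sex TIV CV 8% and a 0.5 SD within-sex TIV gap. The ratio's null rejection at P < 0.0009 was 0.15%, 0.48% and 0.89% for exponents 0.8, 0.6 and 0.4. With TIV as a covariate on raw GMV it was 0.05-0.16% in every scenario examined.

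**The case against.** The strongest reply is that the text never says GMV was divided by TIV. A residual adjustment fits the same words, and the proportionality requirement belongs to the ratio alone. That stands, so the point has to be conditional. A reader might infer that the ROI tests are biased by head size. The documents do not support that: bias would need a ratio, a slope other than 1 and a remaining group difference in TIV, and none of the three is documented.

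A reader might also quote false-positive rates for a conventional 5% test, which look more alarming. The SAP does not test GMV at 5%. At its own threshold the inflation is about 2 to 5 times in relative terms but stays below 1% in absolute terms under the inputs of steps 2 and 3, and a false difference of 1.5-2.5% is small beside the 14% needed for 80% power.

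Head size is also already addressed by the normalisation and, in part, by the gender covariate. Near proportionality little is gained, and the covariate is not free when TIV is unbalanced. All of this stands and limits the point's weight. It does not remove the case for adding TIV: the value is already exported, and adding it protects against a fault of either the ratio or the pooled-residual method.

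**Conclusion.** The point holds in conditional form. The formula is unspecified and TIV is absent from the 54 models. If the formula is a ratio, removal of head size depends on proportional scaling that the plan does not check. If it is a pooled residual, the group effect is attenuated when TIV differs between groups.

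The effect runs from nil (slope 1) to moderate (slope 0.5 or lower, or a TIV gap of several per cent). Every magnitude rests on assumed CVs, slopes, gaps and group sizes, because the documents give none.

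This is a cheap improvement to the MRI part of a study whose title concerns gamma EEG. The EEG ANOVAs and the discriminant analysis, whose four predictors are all EEG measures, are unaffected.

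**What to change.** Three changes to the GMV text:

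1. Add TIV as a covariate beside age and gender in all 54 GMV models. Raw or normalised GMV can be the outcome; once TIV is in the model the group estimates are nearly the same (correlated at 0.996 in simulation).
2. State the normalisation formula.
3. Report TIV by group.

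The Bonferroni threshold is unchanged. No new data are needed, since TIV is already exported.

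The cost is one degree of freedom (36 to 35 at the assumed 20 per group), and about 10% more variance of the group effect if the groups differ by about 5% in TIV. The model also assumes the same GMV-TIV slope in patients and controls, and the SAP should say so.

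### The five EEG ANOVA families carry no covariates although the GMV models adjust for age and gender, which leaves the EEG group effects open to avoidable demographic confounding

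*Combined protocol and SAP*

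**What the plan says.** Under the first EEG heading, the SAP says: "The following EEG measures were analyzed using separate repeated-measures ANOVA including group as a between-group factor and different within-subject factors for" five numbered families. These are power, and intra-hemispheric, midline-to-lateral, midline-to-midline and inter-hemispheric imaginary coherence. Each item lists its own within-subject factors, and none lists a covariate. The scope is wide: "All analyses were performed for total gamma and sub-gamma frequency bands".

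The next paragraph repeats the EEG heading but deals with another outcome: "GMV measures were analyzed with univariate ANOVA". It then says "Age and gender variables were included in the analysis as covariates" and "Bonferroni correction was applied for 54 GMV ROIs". Its first and last sentences are both about GMV, so the covariate sentence reads as applying to GMV only.

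The title sets the contrast: gamma "DISCRIMINATES EARLY-ONSET ALZHEIMER'S DISEASE PATIENTS FROM" healthy individuals. The discriminant analysis enters "a total of four independent variables (three electrode pairs from coherence and one electrode from power analysis) to the model", again with no covariate. The documents contain no participant section, demographic table, sample size or statement on matching.

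**The concern.** The plan treats age and gender as worth adjusting for in one outcome of this group comparison, and leaves them out, without comment, for the outcome that the title is about. Patients and healthy individuals are not randomised to their groups, so nothing in the design itself balances age or gender.

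Two conditions together produce bias: the groups differ on the covariate, and gamma is related to that covariate within groups. If both hold, the unadjusted group main effect mixes a demographic difference with the diagnostic one. The error can go either way, producing an apparent difference or hiding a real one. Age and gender contributions may also partly cancel. Group-by-region tests are affected only if the covariate effect itself varies by region. The discriminant predictors are EEG measures of the same kind, so any such distortion could carry through to them.

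**Working it through.** **The plan's own figure.** The only significance level stated is the GMV one. 0.05/54 = 0.000926, which rounds to the stated 0.0009 (taking 0.05 as the family-wise level, which is not written). It reproduces, and the point does not depend on it. No level is stated for the EEG tests, so 5% is assumed below.

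**Inputs.** From the documents: group is the only between-subject term for EEG; age and gender enter for GMV only; the groups are diagnostic. Assumed, because the documents give nothing: *n* per group, age imbalance *d* (in SD), within-group age-gamma correlation *r*, gender imbalance and gender effect.

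**Step 1: age bias and type I error.** Bias in the unadjusted group effect, in within-group SD of gamma, is *d* × *r*. The type I error is that of a two-sided 5% two-sample t-test with 2*n* − 2 df and non-centrality bias × √(*n*/2). At *n* = 25 and bias 0.32, the non-centrality is 0.32 × √12.5 = 1.13.

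| *d* | *r* | Bias (SD) | 15 per group | 25 per group | 40 per group |
|---|---|---|---|---|---|
| 0.25 | 0.1 | 0.025 | 5.1% | 5.1% | 5.1% |
| 0.25 | 0.2 | 0.05 | 5.2% | 5.3% | 5.6% |
| 0.5 | 0.2 | 0.10 | 5.8% | 6.4% | 7.3% |
| 0.5 | 0.4 | 0.20 | 8.3% | 10.7% | 14.3% |
| 0.8 | 0.2 | 0.16 | 7.1% | 8.6% | 10.9% |
| 0.8 | 0.4 | 0.32 | 13.5% | 19.8% | 29.3% |

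With *d* = 0 or *r* = 0 the bias is zero and the error stays at 5%.

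**Step 2: gender, and both together.** Gender bias is the difference in proportion times the gender difference in gamma. At 25 per group, 0.1 × 0.2 = 0.02 SD gives 5.1%, and 0.3 × 0.5 = 0.15 SD gives 8.2%. Age and gender biases of 0.10 SD each give 10.7% in the same direction (0.20 SD) and 5% in opposite directions (0).

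**Step 3: what adjustment does.** In simulation (50,000 runs for each of 21 cases, with linear and equal slopes), the model with age and gender had a type I error of 4.9% to 5.2% and mean bias within 0.003 SD.

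**Step 4: what adjustment costs in precision.** With *N* = 50 and *R*² the share of within-group variance explained by the covariates, the ratio of adjusted to unadjusted SE is √[(1 − *R*²) × (48/46) × (1 + *d*² × 12.5/48)].
- *d* = 0, *R*² = 0: √(48/46) = 1.022, 2% wider.
- *d* = 0, *R*² = 0.10 or 0.20: 0.969 or 0.914, so 3% or 9% narrower.
- *d* = 0.25, *R*² = 0.16: 0.944, 6% narrower.
- *d* = 0.8, *R*² = 0.01: √(0.99 × 1.0435 × 1.1667) = 1.098, 10% wider.

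**Step 5: unequal slopes.** Take age slopes of 0 and 0.4 with 30 and 20 participants. The common slope is about (29 × 0 + 19 × 0.4)/48 = 0.158, so with no other group difference the adjusted estimate is *d* × (0.4 − 0.158), which is 0.193 at *d* = 0.8. The true group effect then depends on the age at which it is read:
- at the midpoint of the group means, 0.4 × 0.40 = 0.160, leaving a residual bias of 0.033 SD;
- at the pooled mean age, 0.4 × 0.32 = 0.128, leaving 0.065 SD.

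At *d* = 0.25 the same steps give 0.010 and 0.020 SD.

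**The case against.** A reader might infer that the EEG group effects are biased, or are demographic in origin. The documents do not support that. They show neither an imbalance nor a link between age or gender and gamma, and the absence of a participant section is not evidence that the groups were unmatched.

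Several further points have force.

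- **Different outcomes may have different covariates.** GMV also has its own handling of head size through intracranial volume, so adjustment by modality is legitimate and is not a contradiction. What stands is that the choice is unexplained.
- **The magnitude shows how confounding works and says nothing about this study.** With other assumptions (correlation up to 0.5 and 50 per group) the same reasoning reaches about 52%. At 0.25 SD and *r* of 0.1 to 0.2 the error is practically nominal.
- **The title claims both increases and decreases of gamma.** A covariate effect of one sign across all measures could not produce both by itself. This narrows a purely demographic explanation without removing it, since covariate effects may differ by measure or region.
- **The repeated heading might extend the covariate sentence to EEG.** The paragraph's content is against this. If that was the intention, the text needs correcting anyway.

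It is also tempting to require that a difference survive adjustment before it is called disease-related. That goes too far: adjustment does not establish a disease cause, and a non-significant adjusted test may reflect only a wider interval.

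**Conclusion.** The point holds as an avoidable exposure to confounding in the plan. It does not show a biased result. The five EEG families leave out two covariates that the study holds and uses for GMV, in a non-randomised comparison, with no reason given.

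The size for this study is unknown. Under the assumed age range at 25 per group, the type I error of a single 5% test is about 5% to 20%, and the top of that range needs both a 0.8 SD imbalance and a correlation of 0.4. The effect vanishes if the groups are balanced, or if gamma is unrelated to age and gender. The change is worth making because it is cheap, and because it lets a reader see whether the group effects depend on demographics.

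**What to change.** Add to the EEG section of the SAP: *Age (mean-centred) and gender (centred or effect-coded) were entered as between-subject covariates in all five EEG repeated-measures ANOVA families; group effects are reported with and without them.* Fit covariate-by-region terms wherever a group-by-region effect is interpreted. Tabulate age and gender by group and state any matching. Correct the second EEG heading so that the scope of the existing covariate sentence is clear. As the plan is written in the past tense, label the adjusted analysis as added. Report both estimates and interpret a gamma difference with caution where they diverge, without using adjusted significance as a gate.

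**Cost.** One sentence, one table and a rerun across the families and bands, with data already used for GMV.
- Two between-subject error df are lost (48 to 46 at an assumed 25 per group).
- With covariate-by-region terms, each within-subject error term loses twice its effect df. For the 14-level region factor this is 48 × 13 = 624 down to 46 × 13 = 598, a loss of 26.
- The SE may widen, by about 2% with balanced groups and uninformative covariates and up to about 10% at 0.8 SD imbalance.
- If age slopes differ and group sizes are unequal, a common-slope model leaves the residual bias shown in Step 5, so the reference age for the group effect should be stated.

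### No planned EEG test compares the group effect between gamma bands, so significance in one band and not in another would not support a band-specific claim

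*Combined protocol and SAP*

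**What the plan says.** The first EEG block of the SAP specifies "separate repeated-measures ANOVA including group as a between-group factor and different within-subject factors for" five sets of measures. The within-subject factors are:

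- (1) power: anterior-posterior position (4 levels) and laterality (3 levels);
- (2) intra-hemispheric imaginary coherency: region (14) and hemisphere (2);
- (3) midline-to-lateral coherency: midline region (4), lateral region (8) and hemisphere (2);
- (4) midline-to-midline coherency: midline region (3);
- (5) inter-hemispheric coherency: region (10).

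Every factor is a scalp location. Band enters only in the sentence after the list: "All analyses were performed for total gamma and sub-gamma frequency bands". The SAP gives neither the number of sub-bands nor their limits. It states no alpha or multiplicity rule for these ANOVAs; the 0.0009 threshold belongs to the grey-matter volumes and the false discovery rate to the correlations. The correlation and discriminant sections add no comparison between bands. The title refers to "OSCILLATIONS: BOTH INCREASE AND DECREASE OF GAMMA".

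**The concern.** Splitting gamma into sub-bands is informative mainly if the group effect may differ between them, yet nothing in the plan tests that. The only available route to a band-specific statement is to set separate p-values side by side. When each band has moderate power, chance alone will often put one band below the threshold and another above it even though the true effect is the same in both. A reader would then be told that the disease affects one part of the gamma range when the data do not show it.

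A secondary point concerns total gamma. It pools the sub-bands, so a rise in one and a fall in another could offset each other in that particular test.

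**Working it through.** **Is band a factor?** The lists give level counts for the spatial factors of all five measures, and none includes band. The SAP does not literally say one ANOVA per band, but separate ANOVAs, factor lists without band, and a sentence extending all analyses to total gamma and the sub-bands leave no other natural reading.

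**Inputs.** The plan has no figure to reproduce here. The following are assumptions: 20 per group, two-sided alpha 0.05, unit SD in each band, two or three sub-bands, between-band correlation ρ of 0.5-0.7, total gamma as the equal-weight mean of the sub-bands. Simulations used 40,000 replicates per setting unless stated. Each band was tested by a two-sample t-test (the group main effect). Group × band was tested by a t-test on the difference score (two bands) or a repeated-measures F test (three bands).

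**Same true effect in every band, d = 0.64.**

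- Noncentrality per band = d × √(n/2) = 0.64 × √10 = 2.02, so power with 38 df is about 0.505.
- Benchmark with independent bands: two bands disagree with probability 2p(1 − p) = 2 × 0.505 × 0.495 = 0.50. For three bands, 1 − p³ − (1 − p)³ = 1 − 0.129 − 0.121 = 0.75. Positive correlation lowers both.

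| ρ | Two bands disagree | Three bands disagree | Group × band significant |
|---|---|---|---|
| 0.5 | 34% | 51% | 5% |
| 0.7 | 26% | 39% | 5% |

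A wider range (d = 0.6, n = 15-30 per group, ρ = 0.3-0.9, 20,000 replicates) gives disagreement of 14-40% with two bands and 20-61% with three. The interaction test stays at about 5%.

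**Opposite effects, +0.4 and −0.4 SD.**

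- Total gamma: (0.4 − 0.4)/2 = 0, so it rejects in about 5%, which is its alpha. With unequal effects the cancellation is partial: at +0.6 and −0.3 (n = 15-30) total gamma rejects in 7-11%.
- Each sub-band alone: 0.4 × √10 = 1.26, power 0.234. At least one sub-band is significant in about 45-46% at ρ = 0.5-0.7; both are in 1-2%.
- Group × band: the standardised difference is 0.8/√(2(1 − ρ)). At ρ = 0.5 this is 0.80 (power 0.69); at ρ = 0.7 it is 1.03 (power 0.89). At ρ = 0 it is 0.566 (power 0.41), no better than the chance that at least one sub-band is significant, 1 − (1 − 0.234)² = 0.41.

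**Would a sign-only rule do for a rise-and-fall claim?** With +0.8 in one band and 0 in the other, no fall exists. The interaction is nevertheless significant with opposite-signed estimates in 41% (ρ = 0.5) and 47% (ρ = 0.7) of studies. Both bands are individually significant in only about 3%.

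**The case against.** The strongest reply is that the plan announces no band contrast. Repeating an analysis by band is harmless description unless the results are later read as a comparison, and the SAP does not say that they will be. That stands, and it makes the point conditional on such a claim being made.

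A reader might infer from the title that the increase and the decrease lie in different sub-bands. The documents do not say so. The discriminant model combines three coherence electrode pairs with one power electrode, so the opposite directions could equally lie between power and coherence, or between locations. A band interaction would not address either of those.

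A reader might also infer that opposite changes cancel and so escape the plan. They can offset each other only in the total-gamma test, and completely only if weights and effects balance. The sub-bands are tested on their own as well.

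Nor is the interaction always the stronger test. Its advantage disappears at low correlation. For a single-band effect (d = 0.64 in one of three bands) it has about 35% power at ρ = 0.2, against about 50% for that band's own test, although it reaches 52-76% at ρ = 0.5-0.7. Making every per-band result wait for a significant interaction would therefore lose real findings. None of this supplies the missing comparison if a band-specific claim is made.

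**Conclusion.** The concern holds in a limited form. The plan contains no test of whether the group effect differs between gamma bands, so a contrast of significant and non-significant bands would not support band specificity. Under the stated assumptions such a contrast arises by chance in about 26-34% of studies with two bands and 39-51% with three, against about 5% for a direct test. These figures illustrate scale; they are not estimates for this study, because the documents give no sample size, effect size, between-band correlation, band count or EEG alpha. The structural gap does not depend on them.

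The per-band ANOVAs remain valid as tests within each band. Offsetting in total gamma is a caution about reading that one test, not a defect of the whole plan.

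**What to change.** - Keep the per-band ANOVAs. State the number and limits of the sub-bands.
- For each of measures (1) to (5), add one repeated-measures ANOVA with the non-overlapping sub-bands as a further within-subject factor. Leave total gamma out, since it contains them.
- Put power on the log scale and imaginary coherency on one stated common scale. Apply the SAP's existing sphericity rule to the band factor.
- Claim that a group effect is band-specific, or differs between bands, only when group × band (or group × band × region) is significant.
- Claim a rise in one band and a fall in another only when, in addition, each band's own group contrast is significant in its stated direction. Opposite signs alone are not enough.
- Because the plan is written in the past tense, label the added test as a later addition.

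The cost is SAP wording and a little more analysis, with no new data. Some true single-band effects will be reported without a claim of band specificity, because the interaction can have less power than the single-band test when bands are weakly correlated. The rise-and-fall rule is demanding: at ±0.4 SD and 20 per group both contrasts are significant in only 1-2% of studies, and at ±0.8 SD in about 42%.
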